Facility Recruitment																				
Randomization with Baseline Characteristics																				
Committee Approvals																				
Coaching Calls																				
Site Visits																				
Distribute Toolkit																				
Phase in (5-month)																				
Intervention (12-month)																				
Clinician Feedback Reports																				

G. Assessment of Outcome Measures

G.1. Data Sources and Collection

Trial data will not be collected by participating sites. Instead, all variables and outcomes will be obtained from custom extractions from the HCA Healthcare computerized data warehouse. HCA Healthcare has a long-established corporate data warehouse with admission data, demographics, diagnostic and procedure codes, CPOE data, and laboratory and pharmacy data. Trial data from the computerized data warehouse will include demographic, insurer, comorbidity, and laboratory (including microbiology) data for ABD infection cohorts.

G.2. Specifications of the Appropriate Outcome Measures

The primary, secondary and safety trial outcomes are summarized below in Table 3.

G.3. Primary Outcome Measures

The primary trial outcome for ABD infections reflects the national metric of days of therapy (DOT) of extended-spectrum antibiotic use (ES-DOT), which we will evaluate for the empiric period (hospital day 1-3). Trial success will be based upon the relative reduction in this metric between the INSPIRE Stewardship Bundle vs routine care arm when accounting for baseline values.

G.4. Secondary Outcome Measures

There will be two secondary outcomes for ABD infection (antipseudomonal DOT and vancomycin DOT).

G.5. Safety Outcomes

Two safety outcomes will also be assessed. We will evaluate if increased use of standard-spectrum antibiotics causes increased ICU transfers or hospital length-of-stay.

Table 3. Trial Outcomes

Outcome	Metric for ABD Cohort
Primary Trial Outcome: Total Empiric Extended-Spectrum Antibiotic Days of Therapy (ES-DOT)	The number of different extended-spectrum antibiotics each empiric day, summed across the first 3 days of hospitalization. ¹
Secondary Trial Outcomes: Vancomycin Days of Therapy across Empiric Day and Total Empiric Antipseudomonal Antibiotic Days of	The number of days Vancomycin was received on the first 3 days of hospitalization. ¹
	The number of different antipseudomonal antibiotics each empiric day, summed

Therapy (ES-DOT)	across the first 3 days of hospitalization. ^{1,2}

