Subsequent analyses of the primary and secondary outcomes will include both as-treated and adjusted models. Adjusted models will account for individual characteristics such as age, gender, comorbidities, and prior history of MDROs as well as hospital characteristics such as hospital antibiotic resistance. We will also account for seasonality. All adjusters will be determined a priori. These analyses will be reported as point estimates with confidence intervals and without p-values. The reason for including these analyses is to provide additional information related to the trial outcomes for readers to assess the effects of potential confounders. The reason to not include them in a formal multiple comparisons adjustment is because these analyses are non-independent evaluations relative to the as-randomized unadjusted analyses.

We will separately evaluate intervention period effects by arm alone.

Safety Outcomes

Safety outcomes noted in the above table will be assessed in the most conservative manner to identify potential safety issues. Safety outcomes are required because a reduction in ES-DOT might be achieved only by incorrectly withholding ES antibiotics when they were really needed. Each safety outcome will be evaluated for non-inferiority using an as-randomized unadjusted analysis with a one-tailed significance set at alpha = 0.05. Length-of-stay and days to ICU transfer are evaluated within 14 days of admission since empiric antibiotic selection within the first 3 hospital days is not expected to be a main driver of either outcome beyond this time period; evaluation of baseline data also shows that 93% of abdominal patients have length-of-stay equal to or less than 14 days. Analyses planned for these assessments are proportional hazards models with random effects for each hospital and admission. These models are sometimes called frailty or shared frailty models. Because these are safety outcomes, we do not intend to make adjustments for multiple comparisons in testing them, further increasing conservatism.

All analyses will be performed using current versions of SAS (Version 9.4, as of writing, SAS Institute, Cary NC) and/or R (Version 4.0, as of writing).

C.2.11 Power Size/Sample Size Calculations

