Power assessment proceeded as follows, using a Monte Carlo approach.²⁵ We used available data to define a baseline period of 1/1/2019-12/31/2019. In a bootstrap procedure, individuals were selected with replacement from within each hospital, once to represent baseline data and separately to represent “intervention period” data. Hospitals were then “randomized” to intervention or control according to multiple parameters, including number of admissions with abdominal infection and ES-DOT. We then modified the outcomes for the bootstrapped individuals in the “intervention” period in the “intervention” arm to reflect the effect of the intervention.²⁹

We assessed power to identify an overall 12.5% relative reduction in ES-DOT. This effect was implemented by reducing the relative empiric days of therapy for each admission which was exposed to the CPOE prompt. The amount of reduction was a uniform random variate between 0.75 and 1. For example, if the bootstrapped patient initially received 8 ES-DOT and was assigned to have a 12.5% reduction, then that admission intervention ES-DOT would be reduced to 7 days ($8*0.875=7$). The reduction of ES-DOT was selected with a lower bound determined by the investigators as the minimal effect achieved that would be clinically meaningful. Using this method, we have $\geq 99.9\%$ (99.6-99.9%) power to detect this effect.

Since adoption of the intervention will be heavily influenced by the ability to demonstrate safety, our study size was based on the power to detect non-inferiority for safety outcomes. We used methods similar to the above to calculate the power to identify at least a one day increase in length-of-stay for 12.5% of patients who had hospitalizations less than 14 days and found the power was 91.5% (CI 89.6-93.2%), where non-inferiority is defined as a hazard ratio no smaller than 0.98. For days to ICU transfer, we estimated the power to detect a 2% increase in transfers to the ICU on hospital day 3 through 14 to be $>99.9\%$ (CI 99.6-99.9%), where non-inferiority is defined as having a hazard ratio no greater than 1.1 (fewer days to ICU results in a hazard ratio above 1).

For completeness, we note that there are other pre-specified outcomes intended for exploratory analysis in secondary papers for the INSPIRE ABD trial in Table 4 below.

Table 4: Secondary Manuscripts - Other Pre-Specified Outcomes

Secondary Manuscripts (other pre-specified secondary exploratory analyses for later manuscripts)	

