The primary trial analysis will use an as-randomized unadjusted model with two-tailed significance set at alpha = 0.05. Secondary outcomes will be assessed using an as-randomized unadjusted model and will include adjustment for multiple comparisons with two-tailed significance set at alpha = 0.025 for the two secondary outcomes.

Subsequent analyses of the primary and secondary outcomes will include both as-treated and adjusted models. Adjusted models will account for individual characteristics such as age, gender, comorbidities, and prior history of MDROs as well as hospital characteristics such as hospital antibiotic resistance. We will also account for seasonality. All adjusters will be determined a priori. These analyses will be reported as point estimates with confidence intervals and without p-values. The reason for including these analyses is to provide additional

information related to the trial outcomes for readers to assess the effects of potential confounders. The reason to not include them in a formal multiple comparisons adjustment is because these analyses are non-independent evaluations relative to the as-randomized unadjusted analyses.

Safety Outcomes

Safety outcomes are required because a reduction in ES-DOT might be achieved only by incorrectly withholding ES antibiotics when they were necessary. Each safety outcome will be evaluated for non-inferiority using an as-randomized unadjusted analysis with a one-tailed significance set at alpha = 0.05. For length of stay, the non-inferiority margin is a hazard ratio of 0.98. For days to ICU transfer, the non-inferiority margin is a hazard ratio of 1.1 (fewer days to ICU results in a hazard ratio above 1). Analyses planned for these assessments are proportional hazards models with random effects for each time period, hospital, and admission. These models are sometimes called frailty or shared frailty models. Because these are safety outcomes, we do not intend to make adjustments for multiple comparisons in testing them, further increasing conservatism. As above, it may not be possible to include multiple admissions.

All analyses will be performed using current versions of SAS/STAT and/or R packages lme4 and coxme, unless better packages become available in the meantime.

Further Planned Analyses

We note that there are other pre-specified outcomes intended for exploratory analysis in secondary papers for the INSPIRE ABD trial in Table 5 below.

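### The two safety tests are non-inferiority tests, but their rationale and power statement read as a search for harm; 91.5% cannot be non-inferiority power in the length-of-stay scenario named

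*SAP*

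**What the plan says.** The SAP, under Safety Outcomes, fixes the type of test: "Each safety outcome will be evaluated for non-inferiority using an as-randomized unadjusted analysis with a one-tailed significance set at alpha = 0.05". It adds: "For length of stay, the non-inferiority margin is a hazard ratio of 0.98". For ICU transfer the margin is HR 1.1. The sentence on multiplicity, "Because these are safety outcomes, we do not intend to make adjustments for multiple comparisons in testing them, further increasing conservatism", stands in both the SAP and Protocol H.3.

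Other places in the Protocol describe looking for harm:
- G.5: "We will evaluate if increased use of standard-spectrum antibiotics causes increased ICU transfers or hospital length-of-stay".
- H.3, Safety Outcomes: the outcomes will be "assessed in the most conservative manner to identify potential safety issues".
- Power/sample size section: after stating that "our study size was based on the power to detect non-inferiority for safety outcomes", it gives the length-of-stay calculation as "power to identify at least a one day increase in length-of-stay for 12.5% of patients" (those with stays under 14 days), with a result of 91.5% (CI 89.6 to 93.2%).
- Same section, ICU transfer: "we estimated the power to detect a 2% increase in transfers to the ICU on hospital day 3 through 14", with a result above 99.9% (CI 99.6 to 99.9%).

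Neither calculation names the true hazard ratio assumed. Neither document says what an overall statement of safety would require, or what is concluded if one test passes and the other fails. Trial success rests only on the arm-by-period interaction for ES-DOT.

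**The concern.** In a test for harm, a type I error is a false alarm. Leaving several such tests unadjusted makes an alarm easier to raise, which is cautious. In a non-inferiority test the type I error runs the other way: it declares the intervention acceptable when the true effect is at or beyond the margin. Leaving alpha unadjusted is then neutral at best and lenient at worst. The documents specify the second kind of test and defend it with the logic of the first.

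The same mixture reaches the power statement. Power for non-inferiority is the chance of passing when there is no harm, or harm well inside the margin. The Protocol instead describes a harm and a chance of identifying it. If that harm lies beyond the margin, the figure given cannot be non-inferiority power there. This matters because the Protocol says adoption will depend on demonstrating safety and sized the study on this power.

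**Working it through.** **Inputs.** One-sided alpha 0.05, margins 0.98 and 1.1 (SAP Safety Outcomes). Power 91.5%, CI 89.6 to 93.2%; scenario of one extra day for 12.5% of stays under 14 days (Protocol power section). 93% of stays are 14 days or less (Protocol H.3; SAP Trial Outcomes). About 99,000 patients (Protocol Brief Overview). Randomization is 1:1.

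**1. The plan's own figure.** It comes from a bootstrap of 2019 hospital data that the documents do not contain, so it cannot be reproduced. If 1,000 runs were used (an assumption), 915 successes give an exact binomial interval of 89.6 to 93.2%, matching the stated CI. So 91.5% looks like a count of successful runs. The match does not show which event was counted.

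**2. The scenario as a hazard ratio.** Take a daily length-of-stay distribution with P(14 days or less) = 0.93, move 12.5% of stays under 14 days by one day, censor at day 14, and solve for the Cox HR. The shapes are assumptions.

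| Shape | HR (Breslow ties) | HR (Efron ties) |
|---|---|---|
| Exponential | 0.979 | 0.977 |
| Gamma 1.5 | 0.979 | 0.978 |
| Gamma 2 | 0.979 | 0.978 |
| Gamma 3 | 0.978 | 0.977 |
| Log-normal, sigma 0.6 to 0.8 | 0.976 to 0.977 | 0.975 |

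All lie just beyond 0.98. The Protocol speaks of at least one day, so this is the mildest version of the scenario.

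**3. Chance of passing there.** At or beyond the margin, a valid one-sided 0.05 test passes at most 5% of the time. As an unclustered, one-period approximation, events d = 99,000 × 0.93 = 92,070, √d/2 = 151.7, and the pass probability is Φ(ln(HR/0.98) × 151.7 − 1.645):
- HR 0.979: Φ(−0.155 − 1.645) = 3.6%.
- HR 0.975: Φ(−0.776 − 1.645) = 0.8%.

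**4. True HR needed for a 91.5% pass probability.** ln(HR/0.98) = (1.645 + 1.372)/151.7 = 0.0199, so HR = 1.000. If an equal baseline period doubles the variance (√d/2 = 107.3), 3.017/107.3 = 0.0281 and HR = 1.008. A pass probability of 91.5% therefore needs essentially no harm, whatever the length-of-stay shape.

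**5. The two readings cannot be told apart from the documents.**
- Passing at true HR 1: Φ(0.0202 × 151.7 − 1.645) = 92.2% for one period; 69.9% with doubled variance. With 60,000 patients, the other figure in the Protocol Summary: 77.1% and 51.7%.
- Flagging harm at true HR 0.977 against HR 1: Φ(0.0233 × 151.7 − 1.645) = 97.0%; 80.3% with doubled variance.

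With 99,000 patients, 91.5% lies within both ranges.

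**6. ICU transfer.** If the 2% increase is relative, HR is about 1.02, inside the 1.1 margin, and a high pass probability is coherent. If it is absolute, the risk ratio is 1 + 0.02/p, which exceeds 1.1 for any baseline risk p below 20%. The documents do not give p.

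**7. Error rates.** Each test alone: 5%. If both are required for an overall claim, a false overall claim has probability at most 5%. If either pass were enough and both true effects sat at their margins, the chance of at least one false pass would be 1 − 0.95² = 9.75% if independent, 8.8% at an assumed correlation of 0.5, and never above 10%.

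**The case against.** Safety outcomes are often left unadjusted. Here each has its own test, alpha and margin, which already amounts to two separate claims. SAP Table 3 lists them as other pre-specified outcomes, and trial success does not depend on them. All of this stands: no specified test has an inflated error rate.

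A reader might infer from the missing adjustment that the false-safety rate is nearly 10% and that alpha must be split. The documents do not support this. The 9.75% needs an either-or safety claim, which neither document makes, and both true effects at their margins.

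The power paragraph also leans towards non-inferiority: it introduces the calculation that way and defines non-inferiority in the sentence that gives 91.5%. The simple approximation at true HR 1 gives 92.2%. So 91.5% may be a sound pass probability at an unnamed HR near 1. A reader might go further and infer that the figure is miscalculated or the trial underpowered; the documents do not show that either. The approximation ignores clustering and, in its one-period form, the baseline comparison, so it neither confirms nor refutes the bootstrap.

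This defence does not rescue the text. It may justify making no adjustment, but not calling that conservative, and it leaves 91.5% attached to a scenario in which a non-inferiority test should almost always fail.

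**Conclusion.** The point holds in two parts. First, the conservatism claim is wrong for the tests specified. This is an error of rationale: each test keeps its 5% error, and no adjustment is required if both must pass or each is reported as its own claim. Second, and of more consequence, 91.5% cannot be the probability of showing non-inferiority in the length-of-stay scenario the Protocol names. That scenario corresponds to HR 0.975 to 0.979, where a valid test passes less than 5% of the time.

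The HR range rests on assumed length-of-stay shapes anchored at 93% by day 14. The conclusion does not depend on the third decimal, since a 91.5% pass probability would need a true HR of about 1. What 91.5% does measure remains open. The absence of an overall safety rule is missing detail, worth supplying because the Protocol ties adoption to demonstrated safety. The ES-DOT conclusion is unaffected.

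**What to change.** 1. In the Protocol power section, give for each safety outcome the probability of meeting its margin and the true HR assumed (for example HR 1), and say whether the ICU 2% increase is relative or absolute. If 91.5% was a pass probability at another HR, name that HR. If it was the chance of flagging harm, label it so and rerun the existing bootstrap for non-inferiority power.
2. Delete the closing claim of added conservatism from the multiplicity sentence in Protocol H.3 and SAP Safety Outcomes. State that an overall safety conclusion requires both tests to pass, and that otherwise each outcome is reported only as its own claim.
3. The SAP is dated 3/29/2024, after the intervention period ended in December 2023, and the documents do not say whether safety results had been seen. If they had, disclose the rule as a later clarification.

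A two-sided 90% interval beside each margin would match the one-sided 0.05 tests; this is optional reporting, not part of the error.

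**Cost.** Wording only if the stated powers are pass probabilities. Requiring both tests then leaves at least 0.915 + 0.996 − 1 = 91.1% (0.896 + 0.996 − 1 = 89.2% at the lower CI limit). Otherwise, a rerun on existing baseline data is needed and the stated power may fall; the unclustered approximation at true HR 1 spans about 70 to 92% with 99,000 patients. No test, alpha or margin changes.
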